#### Post-randomization care

Participants are referred for standard outpatient management at the end of 8 weeks of randomized care. The blind will be broken by a psychiatrist who is not involved in the patient's care during the study, and depending upon randomized assignment and the response to treatment under randomized assignment, the patient will then have the option of receiving a prazosin prescription at the end of the trial until they re-enter usual care. While study drug and doctor's visits were provided to the participants at no cost during randomization, the cost of medications and doctor's visits will be borne by the participant or their insurance company after they leave randomized care. Weekly phone calls will be made after the last visit until the patient has connected with their care provider.

#### 3.e.5. Measurement of Suicidal Ideation and Behavior

The Scale for Suicide Ideation (SSI) consists of 19 items that evaluate active suicidal desire, specific plans for suicide, and passive suicidal desire.{Beck, 1979 18 /id;Beck, 1997 19 /id;Beck, 1999 20 /id} Each item is rated by the patient on a 3-point scale from 0 to 2 for a maximum score of 38; a lower score indicates less severe suicidal ideation. The SSI will be collected at baseline and at weeks 1, 2, and 4 of randomized treatment, and once by telephone one month after completing randomized treatment. An SSI score >2 predicts increased risk for suicide death over a period of years.{Brown, 2000 314 /id} The SSI will be collected at the start of each visit, before the participant is seen by the study psychiatrist.

The Columbia-Suicide Severity Rating Scale (C-SSRS){Oquendo, 2003 1195 /id} is based upon the Columbia Classification Algorithm of Suicide Assessment(C-CASA).{Posner, 2007 932 /id} This C-SSRS is used by the FDA in clinical trials to assess suicide risk, and includes a structured assessment of past or recent suicidal behavior. It will be administered at each visit by a study psychiatrist blinded to treatment assignment. C-CASA has excellent inter-rater reliability in classifying suicide attempts, with an overall intra-class correlation coefficient of 0.89.

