## **STATISTICAL CONSIDERATIONS**

### 3.f. Statistical Analyses

Outcome measures will be collected at baseline and weekly for the 8 weeks of participation. Repeated measures models will be used to assess the changes over time in suicidal ideation and intensity of nightmares

and disturbing dreams. These models will be used to obtain estimates of the treatment effects (the changes in the outcome measure from baseline to end of randomization), estimates of the variability of the outcome measures at each time adjusted for baseline measures, and estimates of the within patient correlations over time. These estimates will be used in the design of a subsequent adequately-powered randomized clinical trial. Regression diagnostics, residual plots, and exploratory analyses will be done to find appropriate transformations to satisfy the 1) linearity, 2) homogeneity of variances, and 3) normality assumptions. While we assume compound symmetry for the correlation among repeated measures, we will also consider other covariance patterns. We will also assess the correlation amongst all the measures collected over time. While our sample size is small, we will also use a mediation analysis to determine the degree to which nightmares are responsible for (or mediate) the changes in suicidal ideation.{Baron, 1986 1126 /id}{MacKinnon, 2004 1260 /id;Efron, 1979 1261 /id}

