- 3) "Describe procedures in the protocol for managing increases in suicidality, and how research staff is trained and available to provide clinical management"

Response: Managing increases in suicidality is predicated upon detection of such increases. Although we proposed to examine participants weekly, we recognize that suicidal ideation may emerge suddenly and unpredictably. Therefore, research staff will make at least one mid-week phone call to each participant for the first 2 weeks to check on their well-being and assure them that the study staff is available. At each scheduled study visit, the protocol will quantify suicidality 2 ways. First, the participant will complete the

Scale for Suicide Ideation. This information flows from the research staff to study psychiatrists at the time of the visit. Second, the research psychiatrist will administer the Columbia Suicide Severity Rating Scale (C-SSRS), allowing for a thorough review for the presence of any self-injurious behavior since the last visit or the development of any preparatory suicidal planning, as categorized by the C-SSRS.{Oquendo, 2003 1195 /id} Patients judged by the study psychiatrist to be at increased risk of suicide will have an increased frequency of research visits, have smaller supplies of research medication, or may be withdrawn from the study and possibly hospitalized.

- 4) "Have a procedure for emergency coverage that is clearly understood by the clinical research staff, study participants, and families"

**Response:** At the time of consent, participants will receive clear instructions for how to reach study staff during the daytime, and how to access after-hours coverage as provided through each site. Psychiatry residents-in-training who receive emergency calls from participants after-hours will be instructed to call the local principal investigator immediately, regardless of the time of day. The PI or designated co-I will be continuously available to the respective on-call residents to guide crisis management and assess for the primary suicidal endpoints, if necessary by phone.

- 5) "As part of the consent process, consider having explicit discussion with relevant family members, guardians, or friends that includes the risks inherent when study participants are suicidal (risk of death, side effects of treatment)"

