#### **6.g. Research procedures**

Risks of teratogenicity will be limited by obtaining a pregnancy test from each women of childbearing potential before exposure to the first week of outpatient treatment and by counseling on the need for birth control. Pregnancy will be an exclusion criterion for study entry or for continued study participation. The research procedures include weekly assessment of suicidal ideation (the SSI and C-SSRS) and side effects related to medication. A study psychiatrist will examine each participant weekly during routine study visits and will clinically assess the risk of suicide. Participants judged to be at imminent risk of suicide will be managed as described above. Participants will only be given enough study medication to last until their next research visit. The principal investigators or designated co-Is will be available 24-hours per day by phone and beeper in the event of a participant's medical emergency for the entire duration of the trial. Subjects will be provided with a business sized card to carry in their wallets. This card will include contact information for the physicians and staff members. In addition, it will include a 24-hour number to call in case of emergency. This number will put the subject in touch with the Resident-On-Call provided by the Departments of Psychiatry and Health Behavior. The Resident will be able to put the subject in touch with the PI if needed.

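### The week list for the SSI in 3.e.5 stops at week 4, contradicts 3.f, 6.d and 6.g, and if followed leaves the Primary Aim with no week-8 SSI

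*Combined protocol and SAP*

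**What the plan says.** The combined protocol and SAP gives two schedules for the SSI.

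- **Section 3.e.5** is the only place that enumerates SSI weeks: "The SSI will be collected at baseline and at weeks 1, 2, and 4 of randomized treatment". It adds one SSI by telephone a month after randomized treatment ends. Its last sentence on the scale places the SSI at the start of each visit, before the psychiatrist sees the participant.
- **Section 3.f**: "Outcome measures will be collected at baseline and weekly for the 8 weeks of participation". It describes the treatment effects as "the changes in the outcome measure from baseline to end of randomization". It also promises "estimates of the variability of the outcome measures at each time adjusted for baseline measures, and estimates of the within patient correlations over time", and then says: "These estimates will be used in the design of a subsequent adequately-powered randomized clinical trial".
- **Section 6.d, item 3**: "At each scheduled study visit, the protocol will quantify suicidality 2 ways". The first of the two is the SSI, completed by the participant.
- **Section 6.g**: "The research procedures include weekly assessment of suicidal ideation (the SSI and C-SSRS".

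Section 3.e.2 sets weekly visits for 8 weeks, and 3.e.4 puts the final visit at the end of week 8. Table 2 lists the SSI under follow-up visits without week numbers. No statement ranks one schedule above the other.

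**The concern.** The Project Summary makes the effect on intensity of suicidal ideation the Primary Aim. The randomization and blinding text says the most important outcomes are self-reported, and the SSI is the patient-rated ideation scale. So the conflict concerns the main outcome of the trial.

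If the 3.e.5 list is followed, nobody has an SSI at the end of randomization. A week-8 effect could then be obtained only by extrapolating from week 4, while 3.e.2 and Table 1 have the dose still rising over six weeks. The quantities that 3.f intends for planning the next trial, namely variability at each time and within-patient correlation, would not exist for any visit after week 4.

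There is a smaller safety consequence. Sections 6.d (item 6) and 6.h.1 define emergent suicidality as a 6-point rise, and 6.d ties this to SSI scores. That rise could not be checked at visits without an SSI.

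**Working it through.** The plan gives no figure to reproduce here, so the check compares the two sets of assessment weeks.

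**Inputs.** 20 participants (3.e.2). Weekly visits, weeks 1 to 8 (3.e.2, 3.e.4). SSI weeks under the list: {1, 2, 4} (3.e.5). SSI weeks under the other text: {1, …, 8} (3.f, 6.d, 6.g). No dropout is assumed, and the telephone SSI is not counted as on-treatment.

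**Visits without an SSI under the list.** {1, …, 8} minus {1, 2, 4} = {3, 5, 6, 7, 8}, which is 5 of 8 visits, including week 8.

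**Number of on-treatment SSIs.**

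| | Weekly text | 3.e.5 list |
|---|---|---|
| On-treatment SSIs | 20 × 8 = 160 | 20 × 3 = 60 |
| Of these, weeks 5 to 8 | 20 × 4 = 80 | 0 |
| With baseline | 20 × 9 = 180 | 20 × 4 = 80 |

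The difference is 160 − 60 = 100, and 100/160 = 62.5%. The 100 are 80 from weeks 5 to 8 and 20 from week 3.

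**Endpoint.** The effect in 3.f runs to end of randomization, which is week 8. The last listed on-treatment SSI is at week 4, so 8 − 4 = 4 weeks have no measurement. The next SSI is the telephone call a month after treatment. According to the post-randomization care text, the blind has been broken by then and a prazosin prescription may have been offered. That value cannot serve as the week-8 outcome of a randomized comparison.

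**Position within titration.** Week-4 ceiling in Table 1 over the week-6 ceiling: men 10/20 = 50%, women 6/10 = 60%. These are ceilings and not achieved doses. They show only that the list ends before the titration period does.

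**Planning outputs in 3.f.** Post-baseline visit-specific variances fall from 8 to 3. Where a covariance pattern with a separate correlation for each pair of visits is considered, post-baseline pairs fall from C(8,2) = 28 to C(3,2) = 3. Pairs involving week 8 fall from 7 to 0.

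**Medical Monitor (6.e).** On-treatment SSI forms for completed patients at the two reviews: 3 × 3 = 9 instead of 3 × 8 = 24, and 6 × 3 = 18 instead of 6 × 8 = 48.

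**The case against.** The best reply is that this is one stray clause against the rest of the document. Sections 3.f, 6.d and 6.g all point to weekly collection. Table 2 and the last SSI sentence of 3.e.5 fit that reading, so competent staff would probably collect the SSI every week. This stands as a statement about likelihood, and every loss described here depends on the list being followed. It does not remove the contradiction. The list is the instrument-specific instruction for the main outcome, and 3.e.7 gives the same weeks for the HRSD24, so a reader could take it as a deliberate reduced schedule. The sentence about the start of each visit may describe only the order of assessments within a visit. If it does mean every visit, 3.e.5 contradicts itself.

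A second reply is that counting forms overstates the loss of information. This is partly right. Under compound symmetry with correlation ρ, the variance of a mean of k visits is proportional to (1 + (k − 1)ρ)/k. The plan gives no ρ, so take 0.5 to 0.7 as an assumption:

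- ρ = 0.5: 2.0/3 = 0.667 for three visits and 4.5/8 = 0.5625 for eight, about 19% larger.
- ρ = 0.7: 2.4/3 = 0.800 for three visits and 5.9/8 = 0.7375 for eight, about 8% larger.

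The precision of an average is therefore only modestly affected. Compound symmetry, which 3.f assumes first, also needs one correlation under either schedule, so the fall from 28 to 3 matters only for the other patterns that 3.f will consider. Neither point helps with timing: under the list there is no SSI after week 4.

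A third reply is that safety is covered. This largely stands. The C-SSRS is given at each visit and so still rates ideation at week 8, and a psychiatrist examines participants weekly. The withdrawal text in 6.d does not name the SSI, and 6.e sets no SSI threshold for the Medical Monitor.

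**Conclusion.** The concern holds. The 3.e.5 list cannot be reconciled with 3.f, 6.d and 6.g, and the document does not say which governs. Followed as written, the list gives 3 of 8 on-treatment SSIs, none later than week 4, so the change that 3.f sets out to estimate is never observed. The decisive loss is the week-8 value; the 62.5% fall in forms is secondary and assumes no dropout.

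The Primary Aim names neither the SSI nor week 8. Both follow from reading it with the blinding text, 3.e.5, 3.f and the post-randomization care text. The safety effect is limited.

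This must be fixed before enrolment, because a missed week-8 SSI cannot be recovered once a participant has finished, and estimating this effect is the purpose of the pilot.

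**What to change.** In 3.e.5, replace the list of weeks 1, 2 and 4 with every weekly visit through week 8, so that it agrees with 3.f, 6.d and 6.g. In 3.f, state that week 8 is the time point for the SSI effect and that the telephone SSI is outside the randomized comparison. Both are already implied by the end-of-randomization wording, but stating them removes doubt.

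The cost is one corrected clause and one or two sentences. If staff had been working from the list, the change adds 5 self-report forms per participant, 5 × 20 = 100 in all, at visits that already take place. It needs no extra visit, participant, staff member or observer rating.

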#### 3.e.6. Measurement of PTSD symptom severity

The severity of PTSD symptoms will be measured with the PTSD-checklist-specific version (PCL-S). The PCL-S has been shown to have excellent test-retest, internal consistency, convergent and discriminant validity (versus depression), and good sensitivity to change.{Wilkins, 2011 1382 /id} Each participant will complete this self-report scale.

#### 3.e.7. Measurement of Depression

Depression severity will be tracked by the observer-rated 24-item HRSD. {Hamilton, 1960 371 /id;Beck, 1988

337 /id} The HRSD24 will be administered by same project manager, blind to treatment assignment, at baseline and thereafter at weeks 1, 2, and 4 of randomized treatment. Research staff will demonstrate inter-rater reliability  $> 0.85$  against a criterion-set of clinical videotapes. The HRSD24 has three sleep items and one suicide item. The HRSD will be recorded as the total score (HRSD24), and will also be analyzed without the three sleep items or the suicide item (HRSD20). The three insomnia items and the suicide item will be separately examined.

### 3.e.8. Measurement of nightmares: The Disturbing Dreams and Nightmare Severity Scale

The frequency and intensity of disturbing dreams and nightmares will be measured with the Disturbing Dreams and Nightmare Severity Scale (DDNSI). This scale is derivative of a simpler Nightmare Frequency Questionnaire that had a test-retest weighted kappa  $> 0.85$ . {Krakow, 2002 813 /id} The revised DDNSI has good internal consistency with a Cohen's alpha  $> 0.80$ . {Bernert, 2005 798 /id; Bernert, 2009 1044 /id} A DDNSI score  $> 10$  indicates a clinical nightmare disorder. {Krakow, 2002 1368 /id} Each participant will complete this self-report scale.

### 3.e.9. Measurement of insomnia: The Insomnia Severity Index

The Insomnia Severity Index (ISI) is a 7-item self-report measure that examines the intensity of distress associated with night-time and daytime symptoms of insomnia. It is well validated and we have used it extensively in our own research. We have no a prior hypotheses regarding the ISI scale, but include it primarily to provide a complete description of sleep symptoms. {Bastien, 2001 639 /id}

### 3.e.10 Qualitative assessment of nightmares

The VAS scales are designed to tease out any important differences between depressing dreams as reported in depressed patients as opposed to classic PTSD-type nightmares. The VAS scales will be 100 mm long, and will be anchored to the left end with the word 'never', and anchored on the right end with the word 'always'. The participant will be asked to make a single mark on each of several VAS lines relevant to each of the following dimensions of their dreams:

- Repetitive sameness of the dream plot from night-to-night
- Dream content is related to prior real-life traumatic event
- Likelihood of awakening from the dream
- Feeling sad during or after the dream
- Feeling scared during or after the dream
- Feeling angry during or after the dream

### 3.e.11 Blood pressure measurement

Blood pressure will be measured at each REST-ON visit after 5 minutes of quiet sitting, followed by 2 minutes of standing. BP will be measured with an approved automated BP machine.

### 3.e.12 Clinical Global Impression – Severity (CGI-S) and Clinical Global Impression-Improvement (CGI-I)

The participants' overall clinical status and response to treatment will be assessed with the CGI-S and CGI-I. Both scales will be rated along a 7-point dimension. The CGI-S and CGI-I will be completed by a study psychiatrist. The CGI-S will be scored from "Normal" to "Among the most severely ill", while the CGI-S will be scored from "Very much improved" to "very much worse". The CGI-S will be completed at baseline and at all randomized treatment visits, while the CGI-I will be completed only during post-randomization treatment visits.

### 3.e.13. Salivary amylase

In humans,  $\alpha$ -amylase levels are highest in pancreatic and salivary secretions. Increased salivary amylase activity is a marker for increased sympathetic nervous system activity. {Nater, 2009 1466 /id} We will collect samples of saliva at baseline and each follow up visit. The tubes containing the samples will be vortexed, centrifuged at 2000xg at 4 C for 10 minutes, and the saliva will be aliquoted and frozen at -80C for future

analysis. On the day of the assay, the samples will be thawed and will be centrifuged once more to assure that solids are removed from suspension. Salivary amylase activity will be determined using the Amylase Activity Assay kit (Sigma). In this kit, amylase activity is determined using a coupled enzymatic assay, which results in

	Baseline of REST-ON	Follow up Visits in REST-ON	
Evaluation to sign consent	1		
Consent	2		
Registration	3		
Demographics	4		
Visual Analogue scales for nightmare descriptors	5		
Vitals with orthostatic BP	6	1	
PCL-S	7	2	
SCID and CAPS	8		
Hamilton Rating Scale for Depression (HRSD)	9	7	
Beck Suicide Severity Index (SSI)	10	3	
Columbia-Suicide Severity Rating Scale	11	4	
Disturbing Dreams and Nightmare Severity Index	12	5	
Insomnia Severity Index	13	6	
Concomitant Medications	14	8	
CGI-S	15	9	
CGI-I	16	10	
Adverse events		11	
Encounter Disposition Form- Baseline/Baseline Follow-up	17	12	
Study Medication Accountability		13	
Salivary amylase	18	14	
	Baseline of REST-ON	Follow up Visits in REST-ON	
Evaluation to sign consent	1		
Consent	2		
Registration	3		
Demographics	4		
Visual Analogue scales for nightmare descriptors	5		
Vitals with orthostatic BP	6	1	
PCL-S	7	2	
SCID and CAPS	8		
Hamilton Rating Scale for Depression (HRSD)	9	7	

Table 2 – Order of Assessments for REST-ON-PTSD

Beck Suicide Severity Index (SSI)	10	3
Columbia-Suicide Severity Rating Scale	11	4
Disturbing Dreams and Nightmare Severity Index	12	5
Insomnia Severity Index	13	6
Concomitant Medications	14	8
CGI-S	15	9
CGI-I	16	10
Adverse events		11
Encounter Disposition Form- Baseline/Baseline Follow-up	17	12
Study Medication Accountability		13
Salivary amylase	18	14

### 3.e.14 Adverse events

The study psychiatrist will elicit spontaneous reports of adverse events (AEs) and serious adverse events (SAEs) at each treatment visit. In the unexpected event of potentially self-injurious behavior, the behavior will be coded as a suicide attempt according to the Columbia-Suicide Severity Rating Scale (C-SSRS){Oquendo, 2003 1195 /id}, which in turn is based upon the Columbia Classification Algorithm of Suicide Assessment(C-CASA) {Posner, 2007 932 /id}. The C-CASA will be completed by the study psychiatrist and has excellent inter-rater reliability in classifying suicide attempts, with an overall intra-class correlation coefficient of 0.89.

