Tertiary Aims: We will assess the safety of prazosin in the treatment of suicidal PTSD outpatients with nightmares and disturbing dreams. We will assess the impact of prazosin in salivary amylase, which is a test of systemic adrenergic tone.

Impact on the Field This application has the potential to change providers' practice in the approach to treating PTSD patients with mild-moderate suicidal ideation. Physicians have limited options in pharmacologic approaches to reduce suicide risk. The success of prazosin in reducing suicidal ideation in PTSD patients would be a novel strategy for a serious public health problem with few known solutions.

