The American Academy of Sleep Medicine states that the best-practice pharmacologic treatment for nightmares is prazosin.{Aurora, 2010 1365 /id} Prazosin is an  $\alpha_1$  adrenergic receptor blocker approved for use as an antihypertensive. The cardiovascular effects of the drug were fully characterized more than 30 years ago.{Colucci, 1982 1369 /id} The drug is slowly titrated starting with 1-mg capsules in order to minimize the risk of hypotension, with an average dose of 6-15 mg per day for antihypertensive effects. It generally has no effect on heart rate. The most common side effects at these doses are: dizziness 10.3%, headache 7.8%, drowsiness 7.6%, lack of energy 6.9%, weakness 6.5%, palpitations 5.3%, and nausea 4.9%.

A number of randomized controlled comparisons of prazosin have proven that prazosin is superior to placebo in reducing nightmares. These studies have been primarily in the study of PTSD-related nightmares, with some preliminary information suggesting that prazosin may also reduce non-nightmare awakenings in PTSD patients.{Thompson, 2008 1367 /id} The most recent large study of prazosin for PTSD-related nightmares in American soldiers found that a mean bedtime dose of  $15.6 \pm 6.0$  mg in men, and  $7.0 \pm 3.5$  mg in women, reached over a period of 5-6 weeks, was highly effective, with blood pressure changes, as compared with placebo. The most common side effects in this study were lightheadedness (25% versus 20% for placebo) and nasal congestion (22% versus 11% for placebo).{Raskind, 2013 1474 /id}

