### 3.e.4. Treatment

#### Dose finding during randomized care

Participants who pass all screening and baseline-week assessments immediately begin one capsule of prazosin 1 mg capsule or a placebo. Study drug will be taken at bedtime. Participants will be called by study-staff after two nights, and if participants do not appreciate an improvement in their disturbing dreams and nightmares after 2 nights, then they are allowed to increase their bedtime study drug to two capsules, following the design of Raskind et al (Table 1).{Raskind, 2013 1474 /id}

REST-ON participants return to the clinic each week for routine follow up and assessment of treatment response, BP, and adverse events. If the patient and research physician judge the benefit of study drug to be inadequate for sleep continuity or nightmares, then the dose may be increased according to the titration schedule below. At any point during the medication titration, upward dosages will not be permitted if: systolic BP <90, or diastolic <50, either sitting or standing, or if the patient has felt faint or near-syncopal, or has had a syncopal attack. The final research visit will be at the end of the eighth week of randomized treatment, and decisions will be finalized at that time of transition to care as usual.

Table1 Prazosin dose titration schedule

Week/Day	Men's Dose	Women's Dose
Days 1-2	1	1
Days 3-7	2	2
Week 2	4	2
Week 3	6	4
Week 4	10	6
Week 5	15	10
Week 6	20	10

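### Adverse events are taken by spontaneous report with no baseline symptom record, although the safety aim and part of the titration hold rely on faintness and other symptoms

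*Combined protocol and SAP*

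**What the plan says.** The Tertiary Aims in the Project Summary include safety: "We will assess the safety of prazosin in the treatment of suicidal PTSD outpatients with nightmares and disturbing dreams".

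On method, section 3.e.14 states: "The study psychiatrist will elicit spontaneous reports of adverse events (AEs) and serious adverse events (SAEs) at each treatment visit". Two other places promise weekly assessment without saying how it is done. Section 3.e.4: "REST-ON participants return to the clinic each week for routine follow up and assessment of treatment response, BP, and adverse events". Section 6.g: "The research procedures include weekly assessment of suicidal ideation (the SSI and C-SSRS) and side effects related to medication". No section names a checklist or a standard question.

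In Table 2 the row "Adverse events" is empty under baseline and is item 11 under follow-up visits. Both printed copies of the table agree.

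The titration hold in section 3.e.4 has a measured part, "upward dosages will not be permitted if: systolic BP <90, or diastolic <50, either sitting or standing", and a symptom part, "or if the patient has felt faint or near-syncopal, or has had a syncopal attack". It applies throughout titration. The first possible increase follows a staff phone call after two nights.

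The section on randomization and blinding describes a single-blind trial with a placebo that does not match prazosin. It defends this partly on the ground that the most important outcomes are self-reported. Section 3.f describes models for suicidal ideation and nightmares and says nothing about how adverse events will be counted or tabulated.

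**The concern.** Whether someone has felt faint since the last contact can be learned only from that person. If staff rely on what is mentioned, or each word the question differently, the symptom part of the hold is applied unevenly, and the adverse-event counts depend on who asked and how.

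Without a baseline record, a complaint that existed before the first capsule and is first mentioned at week 1 cannot be told apart from a new one. All participants already take an SSRI or a bipolar medication, and the symptoms in section 6.c (such as headache, drowsiness, low energy and nausea) are unspecific.

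Blinding adds to this. Adverse events are elicited in conversation by a psychiatrist, so the self-report argument for a non-matching placebo does not clearly extend to them. Section 3.e.5 calls the study psychiatrist blinded when giving the C-SSRS, but section 3.e.14 does not say so for adverse events.

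The counts are also used during the trial. Under section 6.e the Medical Monitor reviews adverse events after the third and sixth completed patients, and early termination rests on the monitor's judgement that risk has risen systematically.

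**Working it through.** The plan gives no figure for safety that could be reproduced. The check is mainly a reading, with some arithmetic for scale.

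**1. What is and is not captured**

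| Item | Baseline | Two-night call | Weekly visit |
|---|---|---|---|
| Sitting and standing BP (3.e.11, Table 2) | yes | not scheduled | yes |
| Suicidal behaviour by C-SSRS (3.e.5, Table 2) | yes | not scheduled | yes |
| Fainting or syncope, last 6 months (exclusion criteria) | yes | – | – |
| Faintness, near-syncope, lightheadedness | none listed | none stated | spontaneous report |
| Other symptoms in 6.c | none listed | none stated | spontaneous report |

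**2. Where the symptom part of the hold has to work**

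Table 1 allows up to six increases for men (1→2→4→6→10→15→20) and four for women (1→2→4→6→10). The first, from one capsule to two, is decided around the phone call. The only scheduled BP reading available then is the baseline one, taken before the first capsule. At that step any information about the drug's effect must come from symptoms, but the protocol describes the call as being about nightmares, and section 3.e.14 places adverse-event elicitation at treatment visits. At later steps BP is measured at the visit, while near-fainting between visits is known only by history.

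**3. Scale at 10 per arm**

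Inputs: 20 participants randomized 1:1 (section 3.e.2), so 10 per arm. Rates from the PTSD trial cited in section 3.a: lightheadedness 25% on prazosin and 20% on placebo; nasal congestion 22% and 11%. Both are rates during treatment.

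- Expected cases, n × p: lightheadedness 10 × 0.25 = 2.5 and 10 × 0.20 = 2.0; nasal congestion 10 × 0.22 = 2.2 and 10 × 0.11 = 1.1.
- Chance of at least one lightheaded participant, 1 − (1 − p)^10: 1 − 0.75^10 = 94% on prazosin and 1 − 0.80^10 = 89% on placebo.
- One participant misclassified or missed moves an arm's rate by 1/10 = 10 percentage points. The cited differences are 25 − 20 = 5 points and 22 − 11 = 11 points.

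**4. Would better collection allow a formal comparison?**

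Normal approximation, two-sided 0.05, with p̄ the mean of the two rates:

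power = Φ{[d − 1.96·√(2p̄(1 − p̄)/n)] / √[(p₁(1 − p₁) + p₂(1 − p₂))/n]}

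- Lightheadedness: (0.05 − 1.96 × 0.1867)/0.1864 = −1.70, power about 4.5% (exact Fisher 1.1%).
- Nasal congestion: (0.11 − 1.96 × 0.1660)/0.1642 = −1.31, power about 9.5% (exact Fisher 1.6%).
- For 80% power: about 1,094 and 178 per arm.

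So no. The gain is complete counts, a pre-treatment reference and consistent ascertainment.

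**5. Pre-treatment symptoms (assumption)**

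The documents give no pre-treatment rate. If lightheadedness before treatment were 5%, 10%, 20% or 30%, then 20 × rate = 1, 2, 4 or 6 of the 20 participants would have it before the first capsule, and no listed assessment would show it.

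**The case against.** The strongest reply is that section 3.e.14 concerns the recording of adverse events, while the hold is a separate rule that turns on what the patient has felt, not on what a form records. An increase at a clinic visit also needs the patient and research physician to judge benefit inadequate, and nothing says that the physician applies the hold without asking. Weekly side-effect assessment is promised twice, section 6.d adds mid-week well-being calls in the first two weeks, and eliciting implies some enquiry. This largely stands: the enquiry is unstandardised, not shown to be absent. A reader might infer that the hold acts only on what patients volunteer. The documents do not support that, and the BP part needs no symptom report.

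A reader might also take the 20% and 11% placebo rates to mean that these symptoms are common before treatment, or divide them by the prazosin rates to call most prazosin events background. Both go too far. They are rates during treatment, recent fainters and people with a history of hypotension are excluded, and the randomized placebo arm already addresses background that arises on treatment.

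Nor can a number of unrecorded events be derived. The share of events that spontaneous reporting captures is not given, and neither is the way the cited trial collected its events; its rates may themselves be spontaneous reports.

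Finally, open elicitation from first treatment is a recognised choice, and this is a pilot whose purpose is estimating effect sizes. That lowers the weight of the point. It does not supply a baseline reference or a common question.

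**Conclusion.** The point holds as an inexpensive improvement to data collection, not as a failure of the safety plan. The stated method is spontaneous report, no baseline symptom record is listed, and the safety aim and the symptom part of the hold both rely on complaints for which no standard question exists. The gap is clearest at the two-night call.

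Its numerical effect on the counts cannot be stated from the documents. What can be said is that at 10 per arm one case is worth 10 percentage points, which is twice the cited difference for lightheadedness and close to that for nasal congestion. This assumes equal arms and takes the cited rates only as a yardstick. That questioning may differ by arm is a possibility created by the non-matching placebo; the documents do not show that it would happen.

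**What to change.** - Add a one-page fixed symptom list: the nine distinct symptoms in section 6.c (seven from hypertensive patients plus three from PTSD patients, with palpitations in both) and faintness, near-syncope and syncope, so 9 + 3 = 12 items.
- Ask it in the same words of every participant at baseline, at the two-night call and at each weekly visit. Keep the open question for anything else.
- Add the baseline entry to Table 2. State in section 3.f that symptoms new or worse than baseline will be tabulated by arm, descriptively and without a test.
- Reconcile sections 3.e.4 and 3.e.14 on how the symptom part of the hold is ascertained, including at the phone call. The hold rule itself is left as it is.

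Cost: one page and a few minutes per contact. With baseline, one call and eight weekly visits, that is 10 contacts each, or 20 × 10 = 200 short administrations. The downside is that more events will be recorded in both arms, and 10 per arm will still not support a formal comparison of rates.
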